17.3 Vital Sign Assessments

The following vital signs measurements will be summarised at the time points specified in the study schedule of events (Section 24):

- Heart Rate (beats/mins)
- Systolic blood pressure (SBP) (mmHg)
- Diastolic blood pressure (DBP) (mmHg)

- Body Temperature (°C)
- Body Weight

Summary statistics for vital sign parameters in accordance with Section 6.2 will be presented for baseline and for each scheduled post-baseline visit (which also includes change from baseline). These summary tables will be done for Safety Population.

The listing of vital sign parameters will include all the information collected. In addition, the observations that are used as the baseline record (value) for each parameter will be flagged, and the change from baseline values at each post baseline (scheduled and unscheduled) visit will be presented. This listing will be presented sorted by Subject ID and assessment date/time for the Safety Population, along with the age, race, and baseline weight of the subject.

17.4 12-Lead Electrocardiogram (ECG)

The following ECG measurements will be summarised at the time points specified in the study procedure schedule:

- Heart Rate (bpm)
- PR interval (msec)
- QT interval (msec)
- QRS interval (msec)
- QTcF interval (msec)
- Clinical Interpretation

Summary statistics for ECG parameters in accordance with Section 6.2 will be presented for baseline and for each scheduled post baseline visit (which also includes the change from baseline). In addition, clinical result (Normal, Abnormal not clinically significant, abnormal, and clinically significant) will be summarized by counts and percentages for baseline and for each scheduled post baseline visit. These summary tables will be done for Safety Population.

[figure not shown]
The listing of ECG parameters will include all the information collected. In addition, the observations that are used as the baseline record (value) for each parameter will be flagged, and the change from baseline values at each post baseline (scheduled and unscheduled) visit will be presented. This listing will be presented sorted by Subject ID and assessment date/time for the Safety Population, along with the with the age, race, and baseline weight of the subject.

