4.2 Objectives

4.2.1 Primary Objectives and Endpoints

The primary objective of this study is:

The primary objective of the study is to evaluate the safety and tolerability of EQ101 in adult subjects with moderate to severe AA over a 24-week treatment period.

The primary endpoints of this study are:

- Incidence, severity, and relationship of TEAEs, SAEs, TEAEs leading to discontinuation of study treatment.
- Changes in vital sign measurements
- Changes in ECG parameters; and
- Changes in clinical laboratory results.

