6.2 General Considerations

All data collected during the study (data originating from the electronic Case Report Forms (eCRFs) or electronic transfers will be presented in the data listings. Event-based listings will be sorted by subject identifier and event start date/time (i.e., Adverse Event (AE) start date/time). Assessment-based listings will be sorted by parameter name (alphabetically unless specifically stated otherwise), subject identifier, visit, assessment date and time (if applicable).

Unless otherwise stated, the following methods will be applied:

- Continuous variables: Descriptive statistics will include the number of non-missing values (n), arithmetic mean, standard deviation, median, minimum, and maximum values.

The minimum and maximum values will be displayed to the same decimal precision as the source data, the arithmetic mean and median values will be displayed to one more decimal than the source data, and the standard deviation (SD) values will be displayed to two more decimals than the source data for the specific variable.

The appropriate precision for derived variables will be determined based on the precision of the data on which the derivations are based, and statistics will be presented in accordance with the abovementioned rules.

- Categorical variables: Descriptive statistics will include frequencies and percentages per category. The denominator in all percentage calculations will be the number of subjects in the relevant analysis population, unless specifically stated otherwise. Percentages will be rounded to one decimal place and will not be displayed for zero frequencies.
- Repeat/unscheduled assessments: When values collected at scheduled study visits/time points is missing, repeat or unscheduled assessments closest to the scheduled visit date within the visit window defined in Table 1 and Table 2 will be used for the visit to calculate summary statistics in summary tables with visits as defined in section 6.6. All collected data will be included in the data listings. If an unscheduled visit was intended to replace the missing assessment for a scheduled visit this should be documented clearly before values are used as a scheduled visit assessment.

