6.3 Key Definitions

The following definitions will be used:

- Date of the First Study Treatment Administration: The date of the first study treatment administration is defined as the earliest date on which a study treatment was administered.
- Baseline: The Baseline value is defined as the last available valid, non-missing observation for each subject prior to first study treatment administration on Day 1. If day 1 assessment has time missing, it will be considered as the baseline.
- Change from Baseline: The change from Baseline value at each visit will be calculated for all continuous parameters using the following formula when both values are available:

$$\text{Change from Baseline Value} = \text{Result at specified visit} - \text{Baseline Value}$$

- % Change from Baseline: The % change from baseline value is defined as Change from Baseline divided by Baseline value. Study Day: The study day of an event is defined as the relative day of the event starting with the date of the first study treatment administration (reference date) as Day 1 (there will be no Day 0).

The study day of events occurring before the first study treatment administration will be calculated as:

$$\text{Study Day} = (\text{Date of Event} - \text{Date of First Study Treatment Administration})$$

For events occurring on or after Day 1, study day will be calculated as:

$$\text{Study Day} = (\text{Date of Event} - \text{Date of First Study Treatment Administration}) + 1$$

Study days will only be calculated for events with complete dates and will be undefined for events that are ‘Ongoing’ at the end of the study.

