17.2 Safety Laboratory Assessments

For the haematology, serum chemistry and coagulation, continuous data summary statistics (as described in Section 6.2) and count and percentages of normal and abnormal (defined by a test-specific normal range) will be presented for values, change from baseline at each visit.

In addition, Shift from Baseline at each visit for haematology, serum chemistry and coagulation lab parameters (low, normal, high) will also be presented using counts and percentages in shift tables.

For urinalysis and urine microscopy, continuous data summary statistics (as described in Section 6.2) and count and percentages of normal and abnormal will be presented for values at each visit.

The listings of laboratory parameters (haematology, serum chemistry, coagulation, and urinalysis) will include all the information collected. In addition, the observations that are used as the baseline record (value) for each parameter will be flagged, and the change from baseline values (where applicable) at each post baseline (scheduled and unscheduled) visit will be presented. These listings will be presented sorted by Subject ID and assessment date for the Safety Population, along with age, sex, race, and baseline weight of the subject.

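### No planned summary table counts subjects whose ECG interpretation worsened from baseline: SAP 17.4 gives totals by visit only

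*SAP*

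**What the plan says.** SAP 4.2.1 names "Changes in ECG parameters; and" among the primary endpoints, as does protocol 2.2.1. SAP 17.4 lists the ECG measurements to be summarised: heart rate, PR, QT, QRS and QTcF, followed by "Clinical Interpretation".

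The two kinds of measurement are then handled differently.

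- **Numeric parameters:** "Summary statistics for ECG parameters in accordance with Section 6.2 will be presented for baseline and for each scheduled post baseline visit", and the sentence goes on to include change from baseline.
- **Interpretation:** "clinical result (Normal, Abnormal not clinically significant, abnormal, and clinically significant) will be summarized by counts and percentages for baseline and for each" scheduled post-baseline visit. The sentence mentions no change, shift or count of new abnormalities.

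The general definition of change in SAP 6.3 does not fill the gap, because it covers continuous variables only: "The change from Baseline value at each visit will be calculated for all continuous parameters using the following formula when both values are available". The default denominator is in SAP 6.2: "The denominator in all percentage calculations will be the number of subjects in the relevant analysis population, unless specifically stated otherwise".

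For blood tests, SAP 17.2 adds a within-subject display to its normal and abnormal counts: "Shift from Baseline at each visit for haematology, serum chemistry and coagulation lab parameters (low, normal, high) will also be presented using counts and percentages".

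**The concern.** Separate totals at two times show the net result of movement in both directions. A subject who goes from normal to abnormal is offset in the table by one who goes the other way. Dropout has a similar effect. Under the default denominator, a subject with an abnormal baseline ECG who leaves the study lowers the abnormal percentage at later visits although no ECG has normalised.

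The trial has one arm, so a reader judging ECG safety depends on what happened within subjects. The natural question is how many subjects had an ECG that became abnormal, or more abnormal, on treatment. For the interpretation, which can reflect rhythm and morphology findings that the intervals do not describe, no planned ECG table answers it.

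**Working it through.** The documents state no figure that depends on this choice, so there is nothing to reproduce. The check asks how far the planned totals leave the number of newly abnormal subjects undetermined.

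**Inputs.** N = 30, from the approximate enrolment in SAP 4.1. The abnormal counts are assumptions, varied below, because the documents give no ECG abnormality rate. For simplicity the two abnormal categories are pooled.

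**Formula, complete data.** Let b be the number abnormal at baseline, v the number abnormal at the visit, and n the number who moved from normal to abnormal. Then v − n subjects stayed abnormal. This must lie between 0 and b, and n cannot exceed the N − b subjects who began normal. Hence

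max(0, v − b) ≤ n ≤ min(v, N − b).

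**Results with equal totals at both times.**

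| b | v | Planned table shows | Range of n | Maximum as share of 30 | Maximum as share of those normal at baseline |
|---|---|---|---|---|---|
| 3 | 3 | 10.0% and 10.0% | 0 to min(3, 27) = 3 | 3/30 = 10.0% | 3/27 = 11.1% |
| 6 | 6 | 20.0% and 20.0% | 0 to min(6, 24) = 6 | 6/30 = 20.0% | 6/24 = 25.0% |
| 9 | 9 | 30.0% and 30.0% | 0 to min(9, 21) = 9 | 9/30 = 30.0% | 9/21 = 42.9% |

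The upper end is an extreme. It needs every subject abnormal at baseline to normalise while the same number of others become abnormal.

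**With missing visits.** Take 6 abnormal at baseline (6/30 = 20.0%), 4 abnormal at the visit (4/30 = 13.3% with the default denominator) and 3 subjects not assessed. Enumerating all compatible tables gives n from 0 to 4.

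- *n = 0 is possible:* two of the missing subjects were abnormal at baseline and one was normal, and the other four abnormal subjects stay abnormal. The percentage falls by 6.7 points although no ECG changed category.
- *n = 4 is possible:* the three missing subjects were all abnormal at baseline, the other three abnormal subjects normalise, and four normal subjects become abnormal.

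An apparent improvement can therefore coexist with four new abnormalities. A cross-tabulation against baseline gives n directly.

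**The case against.** Four points on the other side have weight.

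1. **The information is in the outputs.** SAP 17.4 also plans a by-subject ECG listing of everything collected, in date order, with the baseline record flagged. With about 30 subjects, worsening can be counted by hand. This stands: the gap lies in the summary tables and not in the data. A reader might infer that the primary endpoint goes unreported for this measure, but the listing shows otherwise.
2. **Most of the endpoint is served.** Heart rate, PR, QT, QRS and QTcF all get change from baseline at each scheduled visit, which is a within-subject comparison. It would be wrong to say that a shift table is the only such comparison available.
3. **Important findings have another route.** Under protocol 6.3.8 the investigator reviews every ECG and documents relevant findings. Protocol 6.3.1 asks for an abnormality to be reported as an adverse event if it has accompanying symptoms or signs, needs further tests or treatment, alters dosing or ends participation, or is judged clinically significant. Such events enter the TEAE tables of SAP 17.1. So the interpretation table is not the only place where a rhythm or morphology finding can surface. This stands, and it confines the gap mainly to new abnormalities rated not clinically significant.
4. **No SAP rule is broken.** Urinalysis and vital signs also get no shift table, and physical examinations are only listed. The blood-test tables therefore show a better format already in use, not a standard that SAP 17.4 violates.

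None of these points supplies the missing count.

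**Conclusion.** The point holds in a limited form. SAP 17.4 tabulates the ECG interpretation as totals at baseline and at each scheduled visit, and no planned summary table gives the number of subjects who worsened, although change in ECG is a primary endpoint. The practical loss is mainly the count of emergent abnormalities rated not clinically significant.

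The illustration gives maxima of 10%, 20% and 30% of 30 subjects, for assumed totals of 3, 6 and 9 abnormal at both times. These are bounds under assumptions, not estimates of what will occur. That totals cannot determine the shift does not depend on them. The reading rests on the visible text of SAP 17.4. The matter is minor.

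**What to change.** Add one sentence to SAP 17.4 planning a shift table of the ECG interpretation (normal; abnormal, not clinically significant; abnormal, clinically significant) from baseline to the worst post-baseline result, and optionally also to Week 24/EOT. The denominator should be subjects with a baseline and at least one post-baseline ECG, with missing results shown separately. State whether the Day 1 post-dose ECG and unscheduled ECGs count towards the worst result. Keep the planned totals by visit. A shift table at every visit would be more than the question needs.

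In the same edit, tidy the category labels: as punctuated, the last one reads as two categories.

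The cost is one extra table from data already collected. A worst-result summary tends to show more abnormalities than any single visit, so a footnote should say this. If the database is already locked, SAP section 3 allows the table as an additional analysis described in the CSR.

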17.5 Physical Examinations

The listing of physical examinations (including full and symptom directed examinations) will include all the information collected. This listing will be presented sorted by Subject ID and assessment date/time for the Safety Population, along with the age, race, and baseline weight of the subject.

18 PHARMACOKINETICS

Plasma concentrations of EQ101 will be provided after DBL. Concentration data can be reported outside the scope of this SAP as additional listings for individual subjects and as statistical summaries grouped by the scheduled timepoint and provided separately after the DBL. The statistical summary may include mean, standard deviation (SD), coefficient of variation (CV%), maximum, minimum, median, geometric mean, and geometric CV%.

[REDACTED]

[REDACTED]

[figure not shown]
[REDACTED]

[REDACTED]

[REDACTED]

[REDACTED]

[REDACTED]

[REDACTED]

[figure not shown]
[REDACTED]

[REDACTED]

[REDACTED]

[REDACTED]

[REDACTED]

23 FINAL ANALYSIS (END OF STUDY)

The final analysis will be conducted after all subjects have completed the study, the clinical database has been locked, and the analysis populations have been approved.

The final analysis will be based on the final version of the SAP. Any deviations from the planned analysis will be documented in the CSR.
